studies by Hardaway et al evaluating fibrinolytic therapy for treatment of ARDS used urokinase and streptokinase, the more contemporary approach to thrombolytic therapy involves the use of tissue-type plasminogen activator (tPA) due to higher efficacy of clot lysis with comparable bleeding risk to the other fibrinolytic agents.

Hypothesis:

We hypothesize that administration of tPA to patients with COVID-19 associated severe ARDS will improve pulmonary gas exchange and oxygenation via a decrease in pulmonary vascular microthrombi.

Study Design:

This is a Phase IIa clinical trial, open label, with a modified stepped-wedge design, testing systemic administration of fibrinolytic therapy with alteplase (tPA) versus standard of care for patients infected with COVID-19 resulting in severe respiratory failure. The design is a rapidly adaptive, pragmatic clinical trial, with 3 interim analyses and 1 final look at the data. Pre-planned adaptations described below will be contemplated at each interim analysis or earlier if recommended by the Data Safety Monitoring Board (DSMB).

Inclusion Criteria: We will include adult patients ages 18-75 years old with known or suspected COVID-19 infection with a PaO₂/FiO₂ ratio < 150 or inferred PaO₂/FiO₂ ratio from SpO₂ if ABG is unavailable (Table) persisting for > 4 hours despite optimal mechanical ventilation management according to each institution's ventilation protocols, and a neurological exam without focal signs or new deficits at time of enrollment (if patient is on paralytics, patient has been aroused sufficiently to allow a neurological examination to exclude new focal deficits or has MRI/CT scan in the last 4.5 hours with no evidence of stroke. Finally, patients must be on the ventilator for ≤10 days to be eligible. Based on experience with critically ill patients, longer ventilation time may be associated with increased risk of bleeding. Patients will be enrolled based on clinical features, without consideration of language (using hospital interpreters and translated consent), race/ethnicity, or gender. A neurological exam or CT/MRI scan to demonstrate no evidence of an acute stroke is needed due to a recent case-report of large-vessel stroke as a presenting feature of COVID-19 in young individuals.⁴⁴

SPO2	FIO2														
	0.3	0.35	0.4	0.45	0.5	0.55	0.6	0.65	0.7	0.75	0.8	0.85	0.9	0.95	1
80%	148	127	111	98	89	81	74	68	63	59	55	52	49	47	44
81%	151	129	113	101	91	82	76	70	65	60	57	53	50	48	45

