- NIAID ordinal scale: The ordinal scale is an assessment of the clinical status as follows: 1) Death; 2) Hospitalized, on invasive mechanical ventilation or extracorporeal membrane oxygenation (ECMO); 3) Hospitalized, on non-invasive ventilation or high flow oxygen devices; 4) Hospitalized, requiring supplemental oxygen; 5) Hospitalized, not requiring supplemental oxygen - requiring ongoing medical care (COVID-19 related or otherwise); 6) Hospitalized, not requiring supplemental oxygen - no longer requires ongoing medical care; 7) Not hospitalized, limitation on activities and/or requiring home oxygen; 8) Not hospitalized, no limitations on activities. (combined items 7 and 8 as our study is limited to hospital)

- 48 hour in-hospital mortality
- 14 days in-hospital mortality
- 28 days in-hospital mortality
- ICU-free days (up to 28 days)
- In-hospital coagulation-related event-free (arterial and venous) days (up to 28 days)
- Ventilator-free days (up to 28 days)
- Successful extubation (no re-intubation for >3 days after initial extubation)
- Successful weaning from paralysis for > 3 days after initial termination
- Survival to discharge

Sample size and Power Analysis: (Pass, 14.0, NCSS, LLC, Kaysville, Utah, USA)

We anticipate that each of the five centers will enroll 8-12 patients. Sample size and power Analysis was conducted using Pass, vs 14.0 (NCSS, LLC, Kaysville, Utah, USA) and focused on the primary outcome as defined above. Sample size assumptions:

- power=80%, confidence=95%, and 4 sequential tests(3 interim+1 final), using the Pocock spending function to determine test boundaries,
- potential improvement assumptions based on a previous study ⁴⁰ with appropriate(e.g., Denver) altitude correction as well as mean baseline PaO₂/FiO₂=149 with an overestimated standard deviation of 100,
- design effect=1.12 due to the study's multicenter nature (intra-class correlation coefficient=0.03, average cluster=5);
- ~20% inflation to account for premature death

A sample size of 50 (25 in each intervention group and 25 in the control group) patients detects a >70% improvement in PaO₂/FiO₂ between intervention groups (both tPA50 and tPA 50 plus drip) and controls, and >91% improvement in PaO₂/FiO₂ between intervention tPA 50 plus drip) and controls. Recruitment will assume at least 30% increase to account for refusal or inability to consent.

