- 2) If at the end of the second intervention deployment (total of 20 patients randomized), the primary outcome improves (PaO₂/FiO₂ ratio at 48 hours) by $\geq 20\%$, or the secondary outcomes PaO₂/FiO₂ ratio at 24 hours improves $\geq 20\%$, or dead space decreases by 15%, or ICU- or ventilator-free days continue to exhibit a positive response (at least 2 days difference), we will modify the mode of administration of the second dose of tPA as follows: following the 50mg tPA bolus, we will initiate a drip of 2 mg/hr tPA over the ensuing 24 hours (total 48 mg infusion) accompanied by an infusion of 500 U/hour heparin during the tPA drip. After this, heparin dose will be increased slowly to maintain a PTT between 60 and 80 sec, titrated per attending's discretion. Interim analyses will be conducted as planned above, and submitted expeditiously to the DSMB, IRB and FDA for approval, yet enrollment will continue while these agencies deliberate and their feedback is received.

See above for the rationale for the tPA50+drip.

Statistical analysis (see attached Statistical Analysis Plan):

All analyses will be conducted initially as an intent-to-treat (patients are analyzed in the group they were randomized to), followed by an as-treated analysis. We will use linear mixed models (continuous outcomes, appropriate transformations if residuals normality departure is detected) or generalized estimating equations (categorical outcomes) to account for intra-hospital cluster effects and repeated measures, with FINAL (OVERALL) significance at $p < 0.05$ (two-tailed tests). If the groups are not comparable, we will compare relative (as opposed to absolute improvement over baseline (with patients as their own controls) to minimize the effect of baseline disparities. In addition, as the sample permits, we will adjust for confounders using a single propensity score adjustor in an inverse probability weighting approach. In addition, we will compare the "dose" of the intervention (i.e., how much of the treatment the patient received) as the effect of interest. The pre-planned final comparisons include within group (improvement over baseline) and between groups, all two-tailed with significance declared according to the alpha defined above by the Pocock spending method.

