### 6.4. Outcomes comparison:

All analyses will be conducted initially as an intent-to-treat (patients are analyzed in the group they were randomized to), followed by an as-treated analysis. The primary outcome will be assessed within group and between groups. Differences in the primary outcome will be assessed using linear mixed models, with appropriate transformations if normality departure of residuals is detected. Linear mixed models allows us to adjust for potential confounders detected in the comparison of the groups at baseline using inverse probability weighting by a propensity score, the covariance structure, the repeated measures and the intra-hospital correlation (as this is a multicenter study). In addition, it tolerates missing observations. We will also compare percent change over baseline, using t-tests with the appropriate adjustment for heteroscedasticity if needed. Categorical outcomes will be compared using generalized estimating equations to account for confounders (as above), covariance structure and intra-hospital correlation. In addition, we will compare the “dose” of the intervention (i.e., how much of the treatment the patient received) as the effect of interest, as premature death is, unfortunately, expected. Survival analysis with inverse probability weighted Cox proportional hazards model and robust sandwich variance estimate with clustering for hospitals will be used for mortality and for survivor-bias outcomes censoring for death (e.g., thrombotic complication). As all outcomes are in-hospital, loss to follow-up is not likely. The pre-planned comparisons include within group (improvement over baseline) and between groups, all two-tailed with significance declared as defined by the Pocock spending method.

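### The Protocol switches the primary outcome to relative change on an undefined finding of baseline non-comparability; the SAP has no such switch, and relative change corrects imbalance only under proportionality

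*Protocol*

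**What the plan says.** Both documents define the primary outcome as the improvement in PaO2/FiO2 from before to after the intervention, at 48 hours after randomization. Neither definition fixes an absolute or a relative scale.

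- **Protocol, Statistical analysis:** "If the groups are not comparable, we will compare relative (as opposed to absolute improvement over baseline (with patients as their own controls". The stated aim is to reduce the influence of baseline differences. No variable, threshold or decision time is given for non-comparability. The next sentence adds propensity-score weighting, but only if the sample is large enough.
- **SAP 6.3:** an absolute standardized mean difference (SMD) above 0.2, or a difference judged clinically relevant, leads to inverse probability weighting. The outcome scale does not change.
- **SAP 6.4:** the primary analysis is a linear mixed model with that weighting. Then: "We will also compare percent change over baseline, using t-tests with the appropriate adjustment for heteroscedasticity if needed". This is an added analysis with no condition attached.
- **SAP 6.2:** every outcome is also to be analysed as change from baseline.

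Neither document names baseline PaO2/FiO2 as a covariate in the primary model.

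**The concern.** The Protocol lets the observed baseline comparison set the scale of the primary outcome, without saying what counts as non-comparable. The SAP handles the same imbalance by another route. Two statisticians following the two texts could report different primary results from the same data.

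The remedy also rests on an unstated assumption. Dividing by baseline cancels a baseline difference only if expected 48-hour PaO2/FiO2 is a constant multiple of baseline. If patients who start low tend to regain more ground, the lower-starting arm appears to improve more, and relative change can enlarge that artefact. The switch acts only in imbalanced trials, which is where this matters.

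**Working it through.** **1. The plan's own figure.** The inputs are "power=80%, confidence=95%, and 4 sequential tests(3 interim+1 final), using the Pocock spending function to determine test boundaries", tests "all two-tailed with significance declared as defined by the Pocock spending method", a baseline mean of 149 "with an overestimated standard deviation of 100", "design effect=1.12", about "20% inflation to account for premature death", and 25 per arm. Simulating the four boundaries in the SAP sample-size table at equally spaced looks gives total power 0.800 and total alpha 0.043, as printed, with a drift of about 3.11. The detectable difference is

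3.11 × 100 × √(2/25 × 1.12/0.8) = 3.11 × 33.47 ≈ 104 points, and 104/149 ≈ 70%.

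This matches the plan. The trial is therefore sized for a difference in points on an SD of 100, then restated as a percentage of 149.

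**2. Bias formulas.** Assume no drug effect and a linear relation of 48-hour to baseline PaO2/FiO2. Let b be its slope, g the ratio of mean 48-hour to mean baseline PaO2/FiO2, and d the baseline difference (tPA minus control). Before any weighting:

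- absolute change: bias = (b − 1)d
- relative change, in PaO2/FiO2 points: bias ≈ (b − g)d

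For g > 1, relative change is the more biased when b < (1 + g)/2. At g = 1 the two are about equal. Near b = g (proportional response) relative change is the less biased.

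**3. Numbers** (assumed control baseline 105, d = −10; positive values favour tPA):

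| b | g | Absolute | Relative, first order | Relative, at arm means |
|---|---|---|---|---|
| 0.5 | 1.00 | 5.0 | 5.0 | 5.5 |
| 0.5 | 1.15 | 5.0 | 6.5 | 7.2 |
| 0.5 | 1.30 | 5.0 | 8.0 | 8.8 |
| 1.0 | 1.30 | 0 | 3.0 | 3.3 |
| 1.3 | 1.30 | −3.0 | 0 | 0 |

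Third row in full: the intercept is 1.3 × 105 − 0.5 × 105 = 84. The tPA arm at 95 reaches 84 + 47.5 = 131.5, a ratio of 1.384. Control reaches 136.5/105 = 1.300. The gap of 8.4 percentage points × 105 ≈ 8.8 points.

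**4. Simulation given an imbalance.** Entry requires "PaO₂/FiO₂ ratio < 150", so the planning mean of 149 with SD 100 cannot describe the enrolled baseline; a truncated baseline (mean about 105, SD about 25) was assumed. Other assumptions: 20 evaluable per arm, tPA arm 0.4-0.8 SD lower (about 12 points), b 0.5-1.0, 48-hour mean 130-150, residual SD 40-60, no drug effect, no weighting, a single look.

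| | Absolute | Relative | Baseline-adjusted |
|---|---|---|---|
| Bias towards tPA (points) | about 0-7 | 4-15 | about 0 |
| One-sided false positives (nominal 2.5%) | about 2-6% | 4-9% | 2-3% |

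An imbalance of that size and direction arises in about 10% of trials at 20 per arm. Without conditioning on it, two-sided type I error is about 5% for all three.

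**5. Power, not conditioned on imbalance.** For an additive effect in the same setting: absolute change and baseline adjustment 76-80%, percent change about 62-74%. With the plan's SD of 100 at both times, 25 per arm, a 70% effect and an assumed correlation of 0.4: absolute 0.91, percent 0.72, adjusted 0.97 with flat controls; 0.91, 0.61 and 0.97 with controls rising 30%. With a proportional response and a 40% multiplicative effect the order can reverse: 0.63, 0.65 and 0.63 in one case, 0.47, 0.64 and 0.51 in another.

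**6. How often the switch could fire.** The Protocol gives no threshold. If the SAP's SMD limit of 0.2 were borrowed, baseline PaO2/FiO2 alone would exceed it by chance in about 48% of trials at 25 per arm, and about 76% at 5 per arm, roughly the first interim look.

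**The case against.** The strongest reply is that relative change may be the right scale. The documents state effects as percentages throughout: the detectable improvement, the adaptation thresholds and the re-bolus criterion. If 48-hour PaO2/FiO2 is proportional to baseline, relative change is unbiased, absolute change is not, and percent change can gain power. No document gives the slope or the control-arm change, and the simulated slopes stop at 1.0, below the reversal points of (1 + 130/105)/2 ≈ 1.12 and (1 + 150/105)/2 ≈ 1.21. This stands. A reader might infer that relative change is worse whenever PaO2/FiO2 rises, or always costs power; neither follows.

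The planned weighting also acts on the same imbalance and is not modelled above, so the bias figures do not describe the full planned analysis. That stands too. But where weighting works the switch is not needed, and the Protocol makes weighting depend on sample size.

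Three further inferences are not supported:

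- **The switch inflates the trial's overall type I error.** Averaged over randomization it was nominal. The single-look 2.5% used here is also not the plan's final nominal two-sided alpha of 0.017.
- **The switch lets the team pick the better result.** As written, the trigger is baseline comparability, not outcome. The weakness is that an undefined trigger cannot be verified afterwards.
- **SAP 6.4 repeats the switch.** Its percent-change t-test is an added analysis.

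**Conclusion.** The point holds in limited form. The Protocol makes the scale of the primary outcome depend on an undefined baseline comparison, the SAP does not, and the two must be reconciled. Relative change does what the Protocol intends only under proportionality, which neither document supports.

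Under regression to the mean with improving controls, it adds bias in an imbalanced trial: by first-order arithmetic the excess over absolute change is (g − 1) times the size of the baseline difference whenever b ≤ 1. A slope below 1 is plausible, because equal SDs at both times make b the correlation. A rise by 48 hours is plausible after selection on low values. Both remain assumptions. The inflation of false positives is modest and conditional on the imbalance.

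Baseline adjustment was essentially unbiased in every linear null scenario examined, including a slope of 1.3, so it does not require the proportionality question to be settled. This is a change that should be made, not a fatal flaw.

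**What to change.** 1. Delete the conditional switch from the Protocol's Statistical analysis section.
2. Prespecify one primary metric in both documents, whatever the baseline comparison shows: the between-arm difference in 48-hour PaO2/FiO2 from the mixed model, with baseline PaO2/FiO2 as a fixed covariate. If a ratio is preferred, use log 48-hour PaO2/FiO2 with log baseline as covariate, and choose this in advance.
3. State in SAP 6.4 that the percent-change t-test is supportive only.

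The cost is wording. Baseline PaO2/FiO2 is needed for eligibility, and a pre-treatment blood gas is already on the schedule for every patient, so no new data are required.

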- 5) the bolus/infusion regimen was employed in the seminal 2001, Hardaway study⁷ demonstrating an improvement in oxygenation in patients with advanced ARDS,

6) the 2mg/ml tPA and 500 U heparin is the standard combination employed by interventional radiology for directed fibrinolysis (personal communication [name], Director of IR, UCSD), and

7) we are reticent to increase the tPA dose to 100 mg considering overall risk: benefit.

The above modification was predicted in the original COMIRB submission, in which we anticipated both dose and mode of administration changes is our adaptive plan.

The rationale and change to a bolus/infusion regimen was discussed with the DSMB, and they concurred without reservation (see letter from DSMB, in which they concur with proposed plan).

[figure not shown]
Design:

This is a multicenter ([name] Shock Trauma Center at Denver Health Medical Center (DHMC), University of Colorado Hospital (UCH), National Jewish Health / St. Joseph Hospital (NJH/SJH), Beth Israel Deaconess Medical Center (BIDMC), Long Island Jewish Hospital / North Shore University Hospital (LIJH/NSUH), Scripps Health (SH), St. Mary's Medical Center (SM), University of Miami (UM), Ben-Taub General Hospital (BT) and Dallas Methodist (DM)) Phase IIa clinical trial. The design is a pragmatic, open label, randomized, controlled, rapidly adaptive clinical trial, with 3 interim analyses and 1 final look at the data. For rapid efficacy assessment to isolate the arm(s) with the highest likelihood of success and lowest bleeding risk, we will deploy each intervention arm sequentially up to each interim analysis, in a modified stepped-wedge fashion, with pre-planned adaptations (below) at each interim analysis. Pre-planned adaptations described below will be contemplated at each interim analysis or earlier if recommended by the Data Safety Monitoring Board (DSMB).

[figure not shown]

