- Heparin dosing for the tPA50 group and for after the 48mg tPA drip in the tPA50 drip group:** An infusion of unfractionated heparin infusion will be continued for up to 7 days or until the patient is extubated and has an O₂ requirement of ≤ 4L/min by nasal cannula, and titrated to maintain the activated partial thromboplastin time to 60-80sec (2.0 to 2.5 times the upper limit of normal) per attending's discretion. In case an additional tPA (alteplase) infusion is needed, the heparin drip should be stopped two hours before and re-started after the alteplase infusion ends, at the same dose as before the alteplase. The goal of this treatment is to prevent recurrent microvascular thrombotic hypoxemia or macrovascular complications (stroke, myocardial infarction or venous thromboembolism) due to possible rebound tPA effects causing hypercoagulability. Intravenous heparin is currently a standard of care (SOC) for COVID-19 patients in the ICU due to their extreme hypercoagulability.

Laboratory Measurements:

1. Arterial blood gases, fibrinogen and D-Dimer levels, PT/INR, aPTT, and CBC. Interval for measurement: before and after tPA IV bolus, 6 hours after the start of the infusion, then every 6 hours for first 24 hours, and once a day for 6 days following treatment intervention in all the groups.
2. Thrombelastography or ROTEM (where available) Interval for measurement: Before and after tPA bolus, 6 hours after the start of the infusion, and every 6 hours for the first 24 hours, then daily thereafter for 6 days or until discharge
3. Troponin and CRP pre-treatment and at 24 hours post-infusion
4. Total Bilirubin test pre-treatment (for baseline liver function)

Laboratory tests will follow the schedule below:

	ABG	CBC with platelet count	PT/INR	PTT	Fibrinogen	D-dimer	TEG or ROTEM	Troponin	CRP	Total Bilirubin
Pre-Treatment	X	X	X	X	X	X	X	X	X	X
After Treatment	X	X	X	X	X	X	X			
Hour 6	X	X	X	X	X	X	X			
Hour 12	X	X	X	X	X	X	X			
Hour 18	X	X	X	X	X	X	X			
Hour 24	X	X	X	X	X	X	X	X	X	
Hour 48	X	X	X	X	X	X	X			
Hour 72	X	X	X	X	X	X	X			
Hour 96	X	X	X	X	X	X	X			
Hour 120	X	X	X	X	X	X	X			
Hour 144	X	X	X	X	X	X	X			
Hour 168	X	X	X	X	X	X	X			

All patients enrolled in the trial, regardless of randomization group, will follow the above lab testing schedule. Total amount of blood to be collected during 7 days of study is 200mL. We are also planning on using the blood and other tissues leftover after the safety labs (discarded samples) for research purposes.

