There will be no adjustment for multiple outcomes, as all were pre-planned. The investigator-statistician in charge ([name]) strongly agrees with the argument that adjustment for multiple comparisons in pre-planned hypotheses leads to more type II errors.^{50,51}

Data Storage:

Data will be captured in the University of Colorado web-based REDCap instrument. The data collection form is in production in REDCap.

Criteria for cessation of administering drugs and safety assessments:

The estimated risk of intracranial hemorrhage is 0.72% ⁴⁵ if total tPA dose is < 1.4 mg/kg over total infusion. Estimated risk of severe or life-threatening bleeding other than intracranial is 0.4% ⁴⁵ if total tPA dose is <1.4mg/kg over total infusion. Per FDA guidelines will deliver bolus over 2 hours.

Specification of Safety Variables

Safety assessments will consist of monitoring and reporting adverse events (AEs) and serious adverse events (SAEs) per protocol. This includes any AE, defined as **any unfavorable and unintended sign (including an abnormal laboratory finding), symptom, or disease temporally associated with the use of an investigational medicinal product (IMP) or other protocol-imposed intervention, regardless of attribution.**

This protocol is limited to infusion of two IMPs, alteplase and heparin and blood sampling; thus given their relative short half-life of infusion drugs alteplase (<72 minutes) and heparin (<90 minutes), any effect listed below manifesting within 3 hours of administration of the intervention drugs would be considered potentially temporally related to the intervention drugs. Adverse events associated with blood sampling are considered temporally related if happening within 30 minutes of the sampling.

Safety check assessments: methods and timing

Serious adverse events and frequency of safety checks are as follows:

Serious Adverse Events	Method for safety check	Safety check frequency	Cessation rule *
Death	NA	NA	NA
Cardio-pulmonary arrest	NA	NA	Any cardio-pulmonary arrest
Allergic reactions including angioedema	Clinical exam	Clinical exam pre, during and immediately post alteplase infusion; every 6 hours post alteplase infusion up to 24 hours; at least every 24 hours after alteplase infusion during heparin infusion or more frequently if any abnormality detected.	Any allergic reaction

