## Section 4: Statistical Principles

**4.1. Level of statistical significance:** see above description of p-value for interim analyses.

**4.2. Description and rationale for any adjustment for multiplicity of time points:** There will be no adjustment for multiple outcomes, as all were pre-planned. The investigator-statistician in charge ([name]) strongly agrees with the argument that adjustment for multiple comparisons in pre-planned hypotheses leads to more type II errors.

**4.3. Analysis populations:** all analyses, including safety analyses, will be conducted initially as **intention-to-treat** and then **as-treated**.

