### **7. Assessment of safety timing and methods and cessation methods**

#### **Specification of Safety Variables**

Safety assessments will consist of monitoring and reporting adverse events (AEs) and serious adverse events (SAEs) per protocol. This includes any AE, defined as **any unfavorable and unintended sign (including an abnormal laboratory finding), symptom, or disease temporally associated with the use of an investigational medicinal product (IMP) or other protocol-imposed intervention, regardless of attribution.**

This protocol is limited to infusion of two IMPs, alteplase and heparin and blood sampling; thus given their relative short half-life of infusion drugs alteplase (<72 minutes) and heparin (<90 minutes), any effect listed below manifesting within 3 hours of administration of the intervention drugs would be considered potentially temporally related to the intervention drugs. Adverse events associated with blood sampling are considered temporally related if happening within 30 minutes of the sampling.

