### Safety check assessments: methods and timing

Serious adverse events and frequency of safety checks are as follows:

Adverse Events	Method for safety check	Safety check frequency	Cessation rule *
Death	NA	NA	NA
Cardio-pulmonary arrest	NA	NA	Any cardio-pulmonary arrest
Allergic reactions including angioedema	Clinical exam	Clinical exam pre, during and immediately post alteplase infusion; every 6 hours post alteplase infusion up to 24 hours; at least every 24 hours after alteplase infusion during heparin infusion or more frequently if any abnormality detected.	Any allergic reaction
Worsening of neurological function	Clinical neurological exam and imaging if applicable per care provider's decision. Most patients will use GCS without verbal component	Clinical exam pre, during and immediately post alteplase infusion; every 6 hours post alteplase infusion up to 24 hours; at least every 24 hours after alteplase infusion during heparin infusion or more frequently if any abnormality detected. Imaging per attending's discretion.	GCS decrease of $\geq 2$ points or focal deficit within 24 hours of study drug infusion or new hemorrhage on CT-Scan or MRI
Worsening of pulmonary function	Arterial blood gas and ventilation indices		$\geq 30\%$ P/FiO 2 baseline reduction
External bleeding	Clinical exam	Clinical exam pre, during and immediately post alteplase infusion; every 6 hours post alteplase infusion up to 24 hours; at least every 24 hours after alteplase infusion during heparin infusion or more frequently if any abnormality detected.	Unresponsive to compression
Gastro-intestinal (GI) bleeding	Clinical exam and hemoglobin	Clinical exam pre, during and immediately post alteplase infusion; every 6 hours post alteplase infusion up to 24 hours; at least every 24 hours after alteplase infusion during	Hemoglobin reduction $> 3\text{g/dL}$ within 24 hours of study drug intervention or requiring RBC transfusion with suspected GI

Serious Adverse Events	Method for safety check	Safety check frequency	Cessation rule *
		heparin infusion or more frequently if any abnormality detected. Endoscopic exam per attending's discretion.	bleeding

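### Adverse events and scheduled bleeding and neurological checks are tied to study drug, so controls have no stated collection period or check schedule and the safety comparison is not like-for-like

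*Protocol*

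**What the plan says.** The Protocol (Specification of Safety Variables) and SAP section 7 define an adverse event as an unfavourable sign, symptom or disease "temporally associated with the use of an investigational medicinal product (IMP) or other protocol-imposed intervention", whatever its cause. The exposures are then listed: "This protocol is limited to infusion of two IMPs, alteplase and heparin and blood sampling". Timing follows: "any effect listed below manifesting within 3 hours of administration of the intervention drugs would be considered potentially temporally related to the intervention drugs". For sampling: "Adverse events associated with blood sampling are considered temporally related if happening within 30 minutes of the sampling".

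The safety-check tables in both documents set clinical examinations before, during and just after the alteplase infusion, then "every 6 hours post alteplase infusion up to 24 hours", then at least daily during heparin. This timing applies to the allergic, neurological, external, GI, hemoptysis, hematuria, retroperitoneal and tube-thoracotomy rows. Death, cardiopulmonary arrest and pulmonary worsening carry no infusion clock.

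Other relevant statements:
- Time zero is randomisation (Protocol, Design; SAP 3.2).
- All arms share one laboratory schedule to hour 168, and patients are followed to death or discharge up to 28 days (Protocol, Laboratory Measurements and Follow-up).
- Controls receive the institution's ARDS protocol, and that definition does not mention heparin. Under heparin dosing, however, the Protocol says: "Intravenous heparin is currently a standard of care (SOC) for COVID-19 patients in the ICU".
- In SAP 4.3, "all analyses, including safety analyses, will be conducted initially as" intention-to-treat, then as-treated.
- The outcome lists include days free of arterial and venous coagulation-related events, but not bleeding.

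**The concern.** A safety analysis by randomised group needs events to be looked for and recorded in the same way in both groups. Here the definition and the examination clock both start from something only the tPA arms receive. A site that follows the text examines tPA patients for bleeding on a schedule and has no corresponding instruction for controls. Because the trial is open label, blinding cannot offset unequal looking.

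The stake is the background rate. These are ventilated, critically ill patients, some probably on heparin, who may bleed without tPA. If their bleeds are recorded less completely, an excess on tPA will look larger than it is. The Data Safety Monitoring Board, which can stop the trial for an unacceptable harm profile, would judge that profile without a reliable comparator. Bleeds not recorded during enrolment may not be reliably recovered later.

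**Working it through.** The plan gives no adverse-event rate or exposure time by arm, so there is no stated figure to reproduce. The comparison below uses the plan's own times.

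**Scheduled clinical checks (bleeding and neurological rows)**
- tPA50 with heparin for the full 7 days: 3 (before, during, just after) + 24/6 = 4 six-hourly + 6 daily (hours 48 to 168) = 13.
- Control: none stated. Counting control heparin as an investigational product does not change this, because the daily checks are also counted from alteplase.

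**Event-related window**
Inputs: 2 h infusion, heparin up to 7 × 24 = 168 h, 3 h after drug, 12 laboratory times, 0.5 h after each sampling.

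| Reading | Control | tPA50 | Ratio |
|---|---|---|---|
| Strict: control heparin is not an investigational product | 12 × 0.5 = 6 h, sampling-related events only | 2 + 168 + 3 = 173 h | 28.8 |
| Strict, heparin for 72 h | 6 h | 2 + 72 + 3 = 77 h | 12.8 |
| Strict, heparin for 24 h | 6 h | 2 + 24 + 3 = 29 h | 4.8 |
| Control heparin counts, given for 7 days | 168 + 3 = 171 h | 173 h | 1.01 |

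For tPA50 plus drip the upper figure is 2 + 24 + 168 + 3 = 197 h, if the 7 days of heparin start after the drip. These hours are windows for linking an event to an exposure. They are not hours of observation.

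**What the two readings could do to the counts**
Assumptions: the true 7-day bleeding risk p is equal in both arms, the hazard is constant, only events inside the window are recorded, heparin runs the full 7 days, and 25 patients on tPA are compared with 25 controls. Then h = −ln(1 − p)/168, and the proportion recorded in controls on the strict reading is 1 − exp(−6h).

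| Assumed p | Expected on tPA, of 25 | Control, strict | Control, heparin counts |
|---|---|---|---|
| 5% | 1.25 | 25 × 0.0018 = 0.05 | 1.25 |
| 10% | 2.5 | 25 × 0.0038 = 0.09 | 2.5 |
| 20% | 5.0 | 25 × 0.0079 = 0.20 | 5.0 |

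The last column applies to controls who receive heparin for the full 7 days. The strict column is an extreme, because it treats the window as a recording cut-off, which the text does not say.

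**Why small differences matter**
The Protocol quotes risks of 0.72% for intracranial hemorrhage and 0.4% for other severe bleeding. The chance of at least one event among 25 is 1 − 0.9928^25 = 16.5% and 1 − 0.996^25 = 9.5%. With counts this low, one or two unrecorded control events would change the comparison.

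**The case against.** The strongest reply is that the 3-hour rule labels temporal relatedness and is not a cut-off for collection. Nothing says later events go unrecorded, and the definition applies whatever the cause. All arms have the same blood counts and coagulation tests to hour 168 and the same follow-up to day 28. Planning an intention-to-treat safety analysis implies that control events are expected. The case report form, which might settle the matter, is not among the documents.

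Most of this stands, and it rules out several stronger readings that a reader might infer:
- **A bleed in a control is by definition not an adverse event.** No passage says so. The text is silent on the collection period, and it names heparin as an investigational product without limiting it to an arm.
- **Controls have some 28 times less observation.** The 6 h and 173 h are relatedness windows, and the gap nearly closes if control heparin counts.
- **Arm selection is distorted.** The stated aim "to isolate the arm(s) with the highest likelihood of success and lowest bleeding risk" concerns which tPA regimen to carry forward, and both regimens share the same adverse-event wording. Dropping an arm rests on events judged attributable to treatment, not on a formal tPA-versus-control bleeding test.
- **The 3-hour and 24-hour windows flatly contradict each other.** The 24-hour limits for a hemoglobin fall and for neurological decline stand in the cessation column. Relatedness and stopping a drug serve different purposes.

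What the reply does not meet is the missing clock. Laboratory tests do not detect hematuria, hemoptysis, external bleeding or a focal deficit. A hemoglobin fall seen in a control still needs a rule that makes it an event.

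**Conclusion.** The point holds as a gap in ascertainment. Neither document gives controls an adverse-event period or a bleeding and neurological check schedule, states the status of their heparin, or lists bleeding as an outcome. Clinically detected events may therefore be recorded less completely in controls, and the safety comparison in SAP 4.3 is not like-for-like. Any bias would run towards overstating tPA harm.

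Its size cannot be fixed from the documents. The window comparison runs from about 6 h against 173 h to about 171 h against 173 h, depending on how control heparin is treated and how long heparin is given. The scheduled-check comparison, up to 13 against none stated, does not depend on that choice.

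A reader might go further and call the comparison invalid, or the tPA excess inflated by construction. The documents do not support that: laboratory results and deaths are comparable across arms, no formal bleeding endpoint or test is specified, and sites may in practice record control events fully.

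**What to change.** In the Protocol's Specification of Safety Variables and in SAP section 7:
1. Define one collection period for adverse and serious adverse events, starting at randomisation, for every randomised patient.
2. Add major bleeding as a safety outcome, defined and recorded identically in both arms from time zero, using the assessment times already scheduled for all patients.
3. State whether heparin given to controls is an investigational product, and record heparin exposure in both arms.
4. Keep the 3-hour window as a relatedness label only, and reconcile it with the 24-hour windows in the cessation table. Which clinical limits apply is for the trial team to settle.

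The cost is wording in two documents and some extra REDCap entries for controls. The laboratory schedule already covers all arms. The plan notes that patients on paralytics may have to be aroused for a neurological examination, so any neurological assessment added for controls would need clinical agreement and could cost more than wording. The recorded control bleeding rate may also be higher than it would otherwise have been. With a common window, equal true risk gives equal expected counts (for example 2.5 of 25 in each arm at an assumed 10%).
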